11.6.6. Columbia-Suicide Severity Rating Scale (C-SSRS)

C-SSRS data will be listed and summarized by visit.

11.6.7. Physician Withdrawal Checklist (PWC)

PWC data will be listed and summarized.

11.7. Other Analyses

Not applicable.

11.8. Interim Analyses

The sponsor expects that approximately 500 subjects across the development program for DS-5565 will need to be exposed to DS-5565 for at least 52 weeks to support registration. If this open-label extension study (DS5565-A-E312) is still ongoing when the above condition is met, the sponsor intends to take a snapshot of the database of this open-label extension study to support registration. The totality of the study data for DS-5565-A-E312 will be analyzed at the conclusion of the study.

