- Medical/surgical history (collected at Screening of the preceding study)
- AEs (any ongoing AEs from the preceding study will be transferred to the database for this extension study)
- Concomitant medications (any ongoing concomitant medications from the preceding study will be transferred to the database for this extension study)
- Vital signs (collected at the End-of-Tapering visit of the preceding study)
- Height (collected at Screening of the preceding study)
- Weight (collected at the End-of-Tapering visit of the preceding study)
- C-SSRS (collected at the End-of-Tapering visit of the preceding study (See Section 9.2.1))
- Clinical laboratory tests (collected at the End-of-Tapering visit of the preceding study)
- Pregnancy test (collected at the End-of-Tapering visit of the preceding study)
- Pain scores (recorded for 7 days prior to the End-of-Tapering visit of the preceding study)

- Sleep interference scores (recorded for 7 days prior to the End-of-Tapering visit of the preceding study)

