9.8. Electrocardiograms

A 12-lead ECG will be conducted at the Screening visit (Visit 1) for de novo subjects, and at Start-of-Treatment visit (Visit 4) and at the End-of-Treatment/Early Termination visit (Visit 21) for all subjects. ECG recordings should be assessed as normal or abnormal, and any abnormal findings should be assessed as not clinically significant or significant. Clinically significant abnormal findings should be reported as medical history (if pre-existent). Refer to Section 9.1 for general guidance on when to report abnormal findings as AEs.

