11.6. Safety Analyses

The safety analysis set will be used for all safety analyses. For safety endpoints, the data from AE assessments, clinical laboratory assessments, physical examinations, 12-lead ECGs, vital signs (including weight) assessments, the C-SSRS evaluation, and the PWC evaluations will be summarized. Preceding study and extension study data will be summarized separately and also may be combined.

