11.6.1. Adverse Event Analyses

AEs will be tabulated using the Medical Dictionary for Regulatory Activities (MedDRA) classification system. A TEAE is defined as an AE that emerges during treatment (having been absent prior to treatment) or worsens relative to the pre-treatment state. For subjects who transfer directly into this study from a preceding study (DS5565-A-E309, DS5565-A-E310, DS5565-A-E311), an AE that started in the preceding study will not be considered treatment-emergent in this study unless the AE worsens in severity during this study. The frequency of subjects experiencing a specific TEAE will be tabulated by system organ class, preferred term, seriousness (see Section 9.3.2), worst severity (see Section 9.3.3), and relationship to study drug (see Section 9.3.4). AEs of special interest

(defined in the SAP) will be summarized separately. In the by-subject analysis, a subject having the same event more than once will be counted only once. Listings of deaths, SAEs, and AEs leading to treatment discontinuation of a subject will be presented.

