11.11. Sample Size Determination

Subjects who complete the double-blind studies are eligible to rollover to this open-label extension study. Although it's unknown how many subjects will complete the double-blind studies, the number is anticipated to be between 2100 and 2500. In addition subjects who did not participate in a preceding double-blind study (referred to as de novo subjects) may be enrolled. Overall, the goal of the open-label extension study is to collect long-term safety data on approximately 500 subjects exposed to DS-5565 for at least 52 weeks. During the conduct of the open-label study, subject withdrawal rates will be closely monitored. Entry into the open-label study will be stopped when the sponsor anticipates that the desired number of subjects completing 52 weeks can be achieved.

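### Could the 11.8 registration snapshot count 52-week exposure that the E312 data do not cover?

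*Combined protocol and SAP*

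**What the plan says.** Section 11.8 expects that "approximately 500 subjects across the development program for DS-5565 will need to be exposed to DS-5565 for at least 52 weeks". If E312 is still open when that happens, the sponsor will "take a snapshot of the database of this open-label extension study to support registration". The complete E312 data are then analysed when the study ends.

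Section 11.11 gives the same figures as a goal for E312 itself, to "collect long-term safety data on approximately 500 subjects exposed to DS-5565 for at least 52 weeks". Entry is to be "stopped when the sponsor anticipates that the desired number of subjects completing 52 weeks can be achieved".

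For rollover subjects, section 6.2.1 states that "any ongoing AEs from the preceding study will be transferred to the database for this extension study", and section 11.6.1 that "an AE that started in the preceding study will not be considered treatment-emergent in this study unless the AE worsens in severity". Section 11.6 adds: "Preceding study and extension study data will be summarized separately and also may be combined". Section 9.8 schedules ECGs "at Start-of-Treatment visit (Visit 4) and at the End-of-Treatment/Early Termination visit (Visit 21) for all subjects", with one more at screening for de novo subjects. The Physician Withdrawal Checklist (PWC) is given only after the last dose (section 9.10.2).

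**The concern.** The trigger in 11.8 is counted across the whole program, but the data released are those of one study. If exposure in a preceding study counts, a subject can be credited with 52 weeks of DS-5565 while E312 holds only 39 of them.

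The missing part would be the period just after DS-5565 was first started. Adverse events that began and resolved then are not in E312, and those carried over unchanged are not treatment-emergent there. A subject counted at Week 39 would also have no ECG after Visit 4. Treatment-emergent adverse events (TEAEs) and ECGs are both named in the primary endpoint (section 3.1.3). At worst, a registration package would claim 52-week exposure that its own tables do not span.

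**Working it through.** **Inputs**
- Trigger: about 500 subjects, 52 weeks (11.8).
- Preceding studies: End-of-Treatment at Week 13 (4.1.2, criterion 12); taper ends at Week 14, the same day as extension Visit 4 (6.2.1).
- ECG at Visits 4 and 21 (9.8); PWC at Week 52.5 and Week 54 (Table 17.1).
- Study length about 39 months (3.1.4); participation 56 or 59 weeks (3.1.5).

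The 500 is a target with no event rate or power behind it, so there is nothing to reproduce. The stated durations do reproduce: 52 + 4 = 56 and 56 + 3 = 59 weeks.

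**1. When a DS-5565-arm rollover subject is counted.** Cumulative count: 52 − 13 = Week 39, or 52 − 14 = Week 38 with the taper week. E312-only count: Week 52. At Week 39, E312 covers 39/52 = 75% of the counted exposure.

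**2. What E312 then holds for that subject**

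| Item | Counted at Week 39 | Counted at Week 52 |
|---|---|---|
| Last scheduled visit | Visit 17 (Week 36) | Visit 21 |
| ECG after Visit 4 | none | Visit 21 |
| PWC | none | none (first at Week 52.5) |
| Preceding-study adverse events | ongoing ones; TEAE only if worse | same |

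The PWC row is the same under both counts, so the counting rule does not cause that gap. For the ECG, the Visit 4 tracing of a DS-5565-arm subject already follows about 13 weeks on drug, and criterion 12 refers to ECGs at the preceding study's Week 13 visit.

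**3. How many counted subjects have not reached Week 52 at the trigger.** The documents do not give the accrual pattern, the share from DS-5565 arms or the withdrawal rate, so these are assumed.

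*Simple version* (even entry, all 500 from E312, no withdrawal): 39 × 365.25/12/7 = 169.6 weeks; 169.6 − 59 = 110.6 weeks of entry; 500/110.6 = 4.52 per week; × 13 = 59 subjects (12%), or 29 (6%) if half had earlier DS-5565. With entry over 52 weeks: 500/52 × 13 = 125 (25%), or 63 (13%).

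*Fuller version*: N entrants evenly over A weeks, share f from DS-5565 arms, proportion d withdrawn by Week 52 at a constant rate. The number counted at time t is the sum of
- f × (entered at least 39 weeks ago) × (1 − d)^(39/52)
- (1 − f) × (entered at least 52 weeks ago) × (1 − d)

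Example: N = 2300, A = 52, f = 0.67, d = 0.3, t = 58.5. Entry is 2300/52 = 44.23 per week. First term: 0.67 × (19.5 × 44.23) × 0.765 = 442. Second term: 0.33 × (6.5 × 44.23) × 0.7 = 66. Total about 509. Reached Week 52: 287.5 × 0.7 = 201.

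Over N = 1000 to 2300, A = 52 to 108 and d = 0.3 or 0.5:
- f = 33% to 67%: 201 to 457 of about 500 had reached Week 52, leaving about 44 to 307 who had not.
- f = 100%: 62 to 376 had reached it.
- E312-only count: all had reached it.

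The remainder includes some subjects who stopped between Weeks 39 and 52 and so are due the early-termination ECG. The number with no later ECG is therefore smaller still.

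**4. Effect on incidence.** Under constant risk, cutting every subject off at Week 39 turns a 52-week incidence of 10% into 1 − 0.90^0.75 = 7.6%, and 30% into 1 − 0.70^0.75 = 23.5%. That overstates the effect, because counted subjects short of Visit 21 lie between Weeks 39 and 52. At the 45.5-week midpoint the figures are 8.8% and 26.8%. If 12% of counted subjects are in that window, 10% becomes 0.88 × 10 + 0.12 × 8.8 = 9.9%; if 60% are (307/509), it becomes 0.4 × 10 + 0.6 × 8.8 = 9.3%. The safety tables also use everyone dosed (11.1, 11.6), not the counted 500, so incomplete follow-up affects any snapshot of a running study, whichever clock is used.

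**5. Where the first 13 weeks are reported.** Section 11.6 makes the separate summary of preceding-study data a commitment; only the combined one is optional. Section 11.8 does not say that the snapshot will be read alone. It mentions the E312 database because E312 is the study that may still be running.

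**The case for a change.** The best case for a change is that the cumulative reading is a natural one. Section 11.8 is program-wide, section 3.1.1 arranges rollover so that treatment is not interrupted, and both doses are used in the preceding studies. The phrase in 11.11 about completing 52 weeks governs when entry stops, not when the snapshot is taken.

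The two measures in 11.11, exposure and completion, can differ even inside E312. Dosing runs from the evening of Visit 4 to the evening before Visit 21, whose window is ±7 days. A subject seen a week early therefore completes with 364 − 7 = 357 dosing days, or 51 weeks. For rollover subjects, baseline laboratory values, vital signs and weight come from the End-of-Tapering visit, so E312 change tables also leave out change during the first DS-5565 period. Early terminators do have a Visit 21 ECG, but those who stop before 52 cumulative weeks cannot fill a gap in the 52-week group.

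All of this stands as description. It shows that a rule in days from a stated first dose would be tidier. It does not show a wrong result: the target is approximate, the early data are collected and summarized in the preceding studies, and no inference depends on which clock is chosen.

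**Conclusion.** No change to the plan is needed. Sections 11.8 and 11.11 leave a counting definition unwritten, and the analyst must settle it to derive exposure at all. Section 11.2 leaves methodological detail of this kind to the SAP.

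On an E312-only count the effect is zero. On a cumulative count, a DS-5565-arm rollover subject is counted 13 weeks earlier (14 with the taper week). At that moment the subject lacks the Visit 21 ECG, and E312 alone lacks the resolved preceding-study events and does not class unworsened ongoing ones as treatment-emergent. This is a gap for individual subjects at the time of counting, not for the whole snapshot. The numbers affected depend on accrual, arm share and withdrawal assumptions that the documents do not supply, and on all counted subjects coming from E312, whereas 11.8 counts across the program.

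The analyses are descriptive, the first 13 weeks have their own planned summary, and the final analysis covers all E312 data. Following the plan as written leads to no demonstrated error.

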11.9. Data and Safety Monitoring Board

An independent DSMB will be responsible for providing independent recommendations to the sponsor about evolving risk-benefit observed in the course of the double-blind preceding studies and this open-label extension study. The DSMB will review safety data in an ongoing manner to monitor and assure overall safety of the study subjects. In accordance with an agreed-upon charter, the DSMB will meet periodically, on a regular and/or ad hoc basis, to discuss and address any emerging safety or tolerability issues, including SAEs, discontinuations due to AEs, etc., as well as other relevant study information, such as recruitment status, ineligibility rates, and data quality. Based on any formal DSMB review meeting where safety data are reviewed and discussed, the DSMB will recommend to the sponsor one of the following:

- Continue the study without modification
- Continue the study but modify the protocol and/or the ICF
- Suspend the study (or a cohort) until further notice, with recommendations for further action to address specific issues and appropriately managing active study subjects
- Terminate the study (or a cohort) with provisions for orderly discontinuation in accordance with GCP.

Modification, suspension, or termination may be made for any of the following reasons:

- Concern about drug-induced liver injury
- Concern about suicide
- Any other safety concern

The approach to study (or a cohort) modification, suspension, or termination will be described in the DSMB charter.

The sponsor (Head of Clinical Safety and Pharmacovigilance) will be notified of the DSMB decision by the DSMB chairman within 3 days after the meeting. Minutes of all formal DSMB meetings and discussions will be maintained by the independent statistician, in a secure location, until completion or termination of the study, at which point they will be forwarded to Daiichi Sankyo for archiving.

11.10. Hepatic Adjudication Committee

The HAC will comprise at least two qualified hepatologists, who are not investigators in the study and not otherwise directly associated with the sponsor. The HAC will follow its own charter for processing and adjudicating hepatic events. This adjudication will be independent of the investigators. The HAC will complete assessments on an ongoing basis. Adjudication of hepatic events will be based on evaluation of eCRFs and source documents, as available, including but not limited to hospital discharge summaries, diagnostic imaging, histopathology, consultation, and laboratory reports.

11.11. Sample Size Determination

Subjects who complete the double-blind studies are eligible to rollover to this open-label extension study. Although it's unknown how many subjects will complete the double-blind studies, the number is anticipated to be between 2100 and 2500. In addition subjects who did not participate in a preceding double-blind study (referred to as de novo subjects) may be enrolled. Overall, the goal of the open-label extension study is to collect long-term safety data on approximately 500 subjects exposed to DS-5565 for at least 52 weeks. During the conduct of the open-label study, subject withdrawal rates will be closely monitored. Entry into the open-label study will be stopped when the sponsor anticipates that the desired number of subjects completing 52 weeks can be achieved.

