4.2.3. Subject Replacement

Subjects removed from the study for any reason will not be replaced.

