6. STUDY PROCEDURES

A study visit schedule in tabular format is provided in [Appendix Section 17.3](#).

Subjects will receive open-label treatment for 52 weeks followed by 4 weeks of post-treatment follow-up. The screening/baseline process will depend on whether the subject is a rollover subject or de novo subject. De novo subjects will have a Screening visit (Visit 1) and also complete Visits 2 and 3 (as detailed in [Section 6.1.2](#)) before receiving study treatment at the Start-of-Treatment visit (Visit 4). Rollover subjects will have screening procedures performed at the Start-of-Treatment visit (Visit 4), which will occur on the same day as the End-of-Tapering visit of the preceding study (as detailed in [Section 6.2.1](#)). All subjects will visit the clinic the following week (Visit 5, Week 1); every 2 weeks thereafter for the next 12 weeks (Weeks 3, 5, 7, 9, 11, and 13); 3 weeks thereafter (Week 16); every 4 weeks thereafter for the remainder of the study (Weeks 20, 24, 28, 32, 36, 40, 44, 48, and 52); and at the post-treatment follow-up visit (Visit 23, Week 54). Post-treatment follow-up will also include telephone contacts at 3 days (Visit 22) and at 4 weeks (Visit 24) after the subject's last dose of study treatment.

NOTE: The MINI and C-SSRS are to be administered at any time during the study (including unscheduled visits) based on investigator's discretion ([Section 3.1.6.1.2](#)).

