6.2.2. Start-of-Treatment Visit for De Novo Subjects

For de novo subjects, the following activities and/or assessments will be performed at the Start-of-Treatment visit (Visit 4; Week 0).

- Assess for and record AEs
- Record any concomitant medications used since the last visit
- Review subject's electronic daily diary data and ask subject to complete pain and sleep interference ratings for today (Day 1), if not yet completed
- Assess subject eligibility using the study's inclusion/exclusion criteria, including Baseline ADPS from daily diaries (a minimum of 4 daily pain ratings must be available)
- Administer the C-SSRS and evaluate for eligibility (See Section 9.2.1)

If the subject is found to be eligible based on the results of the ADPS and C-SSRS assessments, proceed to perform the following procedures:

- Record body weight and vital signs (temperature, heart rate, supine and orthostatic blood pressure)
- Perform abbreviated physical examination (see Section 9.9.2)
- Collect blood and urine samples for evaluation of standard laboratory safety tests (chemistry, hematology and urinalysis). An additional 8.5 mL serum separating tube of blood will be collected at Day 1 and stored for further analysis in the event of AST or ALT elevations $\geq 3 \times \text{ULN}$ during the study (see Section 9.2.2)
- The central laboratory will perform a serum pregnancy test on all female subjects regardless of child-bearing potential
- Ask subject to complete the HADS, SF-36 and EQ-5D questionnaires
- Provide additional training on recording of pain and sleep interference ratings for any subjects who had errors or missing information during the Baseline Period
- Contact IXRS to obtain the subject medication wallet number
- Dispense study medication wallet and review dosing instructions with the subject. The first dose of study medication is to be taken on the same day as the Start of Treatment visit, at bedtime after completion of the study visit. Subjects should be instructed to bring their study medication wallet with them to each clinic visit

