6.3. On-Treatment Period (Visits 5 to 20; Weeks 1 to 48)

The following activities and/or assessments will be performed at all On-Treatment visits (except where otherwise noted):

- Assess for and record AEs
- After 3 weeks on the 15 mg QD dose (at Visit 6, Week 3), subjects will be asked about the adequacy of their pain control and may be dose-escalated to DS-5565 15 mg BID (see Section 5.1.1)
- Assess for and record concomitant medication use including allowable analgesics
- Review instructions with the subject for completion of the pain and sleep interference diary. Note: These instructions need to be reviewed with the subject only at Visit 10 (Week 11), Visit 13 (Week 20), Visit 16 (Week 32), Visit 19 (Week 44), and Visit 20 (Week 48)
- Review electronic diary data from the previous week. Note: These data need to be reviewed only at Visit 11 (Week 13), Visit 14 (Week 24), Visit 17 (Week 36), Visit 20 (Week 48), and Visit 21 (Week 52)
- Collect study medication wallets and review medication compliance
- Record vital signs (temperature, heart rate, supine and orthostatic blood pressure) and body weight
- Complete the C-SSRS and evaluate for continued eligibility (See Section 9.2.1)
- Perform an abbreviated physical examination for all subjects; perform a funduscopy examination without pupil dilation or a scanning laser ophthalmoscopy examination at Visit 14 (Week 24) for de novo subjects (see Section 9.9.2)
- Collect non-fasting blood and urine samples for evaluation of standard laboratory safety tests (chemistry, hematology, and urinalysis). The central laboratory will perform a serum pregnancy test on all female subjects regardless of child-bearing potential
- Contact IXRS and obtain new study medication wallet number (as needed)
- Dispense study medication and review dosing instructions. At Visit 20 (Week 48), subjects should be instructed to take all study medication, as scheduled, up until the day of their End-of-Treatment visit (Visit 21, Week 52), but not on the morning of Visit 21 (i.e. subjects should complete dosing on the evening prior to their End-of-Treatment visit)

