17.3. Schedule of Events

Table 17.1: Schedule of Events

Study Period	Screening/Baseline (De Novo Only)			Start of Tx	on-Treatment				End of Tx/Et	Follow-Up ^a		
	1	2	3		4	5	6-11	12		13-20	21	22
Telephone Contact	--	X	--	--	--	--	--	--	--	X		X
Week	-3	-2	-1	0	1	3, 5, 7, 9, 11, 13	16	20, 24, 28, 32, 36, 40, 44, 48	52	52.5	54	56
Visit Window (Days)	--	--	--	--	±3	±3	±3	±7	±7	±1	±3	±7
Informed consent	DN			X ^b								
Inclusion/exclusion	DN			X								
Demographic information	DN			X ^b								
Medical/surgical history	DN			X ^b								
Adverse event reporting		DN	DN	X ^c	X	X	X	X	X	X	X	X
Washout instructions		DN										
Concomitant medications	DN	DN	DN	X ^c	X	X	X	X	X	X	X	X
Vital signs	DN			X ^d	X	X	X	X	X		X	
Height	DN			X ^b								
Weight	DN			X ^d	X	X	X	X	X		X	
Physical examination ^e	DN			X	X	X	X	X	X			
Fundoscopy ^e	DN							DN (V.14)	DN			
C-SSRS	DN			X ^d	X	X	X	X	X		X	
WPI/SSS	DN											

Study Period	Screening/Baseline (De Novo Only)			Start of Tx	on-Treatment				End of Tx/Et	Follow-Up ^a		
	1	2	3		4	5	6-11	12		13-20	21	22
Telephone Contact	--	X	--	--	--	--	--	--	--	X		X
Week	-3	-2	-1	0	1	3, 5, 7, 9, 11, 13	16	20, 24, 28, 32, 36, 40, 44, 48	52	52.5	54	56
Visit Window (Days)	--	--	--	--	±3	±3	±3	±7	±7	±1	±3	±7
M.I.N.I	DN											
12-lead electrocardiogram	DN			X					X			
Clinical laboratory tests	DN			X ^d	X	X	X	X	X			
Pregnancy test ^f	DN			X ^d	X	X	X	X	X		X	

Table 17.1: Schedule of Events (Continued)

Study Period	Screening/Baseline (De Novo Only)			Start of Tx	on-Treatment				End of Tx/Et	Follow-Up ^a		
	1	2	3		4	5	6-11	12		13-20	21	22
Telephone Contact	--	X	--	--	--	--	--	--	--	X		X
Week	-3	-2	-1	0	1	3, 5, 7, 9, 11, 13	16	20, 24, 28, 32, 36, 40, 44, 48	52	52.5	54	56
Visit Window (Days)	--	--	--	--	±3	±3	±3	±7	±7	±1	±3	±7
PWC										X	X	
Study drug compliance					X	X	X	X	X			
Contact IXRS	DN			X	X	X	X	X	X			
Study drug dispensing ^g				X	X	X	X	X ^h				
PGIC									X			
HADS				X					X			
EQ-5D and SF-36				X					X			
Provide daily diary			DN									
Review/collect daily diary				X ⁱ		X ⁱ		X ⁱ	X ⁱ			
Pain intensity rating				X ⁱ		X ⁱ		X ⁱ	X ⁱ			
Sleep interference score				X ⁱ		X ⁱ		X ⁱ	X ⁱ			

DN denotes visits and assessments for de novo subjects only.

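### Does closing entry on subjects completing 52 weeks, when the goal is at least 52 weeks of exposure, put the target of about 500 at risk?

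*Combined protocol and SAP*

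**What the plan says.** Section 11.11 sets the aim of the extension as "long-term safety data on approximately 500 subjects exposed to DS-5565 for at least 52 weeks". After noting that withdrawal rates will be monitored, it gives the rule for closing recruitment: "Entry into the open-label study will be stopped when the sponsor anticipates that the desired number of subjects completing 52 weeks can be achieved". The synopsis carries both statements.

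Section 11.8 deals with the registration snapshot and uses the same figure at another level: "approximately 500 subjects across the development program for DS-5565 will need to be exposed to DS-5565 for at least 52 weeks".

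The length of treatment is fixed in Section 6: "Subjects will receive open-label treatment for 52 weeks followed by 4 weeks of post-treatment follow-up". Sections 6.2.1 and 6.2.2 place the first dose at bedtime on the day of Visit 4 ("The first dose of study medication is to be taken on the same day as the Start of Treatment visit"). For the end of treatment, Section 6.3 says that "subjects should complete dosing on the evening prior to their End-of-Treatment visit". The Schedule of Events (Section 17.3) allows 7 days either side for the Week 52 visit, Visit 21.

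The protocol does not define completing 52 weeks. It does not say how exposure days or gaps are counted, or whether DS-5565 taken in a preceding study counts toward the 52 weeks. Section 11.6 says only that preceding and extension data will be summarised separately and may also be combined.

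**The concern.** The goal is a minimum length of exposure, while the closing rule refers to completion. The dosing instructions leave no margin between them. A subject seen on the nominal day has exactly 52 weeks of dosing, so the threshold lies at the centre of the visit window. A visit one day early, which the schedule permits, puts a subject below it. If completion means an in-window Visit 21 and the goal is read to the exact day, the closing rule can be met while the goal in the same paragraph is missed.

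The 500 is the study's only numerical target, and Section 11.8 ties the same number to registration. Entry closes during conduct. The SAP promised in Section 11.2 covers the final analysis, so a shortfall seen at that stage could not be made good by further recruitment into this study.

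**Working it through.** **Inputs.** Goal of about 500 at 52 weeks or more (Section 11.11); first dose on the Visit 4 day (6.2.1, 6.2.2); last dose on the evening before Visit 21 (6.3); window of ±7 days (17.3); End-of-Treatment at Week 13 in the preceding studies (exclusion criterion 12, Section 4.1.2); 2100 to 2500 anticipated double-blind completers (11.11). The 500 has no power, event-rate or dropout calculation behind it, so there is no formula to reproduce.

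**Step 1: days of dosing.** Count Visit 4 as day 0. Doses run from day 0 to the day before Visit 21, so the number of dosing days equals the day of Visit 21. The threshold is 52 × 7 = 364 days.

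| Visit 21 | Dosing days | Weeks |
|---|---|---|
| 7 days early | 357 | 51.0 |
| 1 day early | 363 | 51.9 |
| nominal | 364 | 52.0 |
| 7 days late | 371 | 53.0 |

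This assumes that windows are anchored to Visit 4, which the schedule does not state. If each window ran from the previous visit, the outer limits would be 364 ± (8 × 3 + 9 × 7) = 364 ± 87, or 277 to 451 days.

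**Step 2: effect on the count, extension exposure only.** Let s be the share of completers whose Visit 21 falls before day 364. Of 500 completers, 500 × (1 − s) reach 364 days, and 500/(1 − s) completers are needed for 500 to do so. The documents do not give s; the values below are assumptions.

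| s | At ≥364 days, of 500 completers | Completers needed |
|---|---|---|
| 0% | 500 | 500 |
| 10% | 450 | 556 |
| 25% | 375 | 667 |
| 7/15 = 46.7% (uniform over the 15 days) | 267 | 938 |

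The last row illustrates evenly spread visits and is not a forecast. Even 938 completers would be 938/2100 = 44.7% to 938/2500 = 37.5% of the anticipated double-blind completers, before any de novo subjects.

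**Step 3: prior exposure.** The goal concerns exposure to DS-5565 and is not expressly limited to this study. Both doses are being tested in the preceding studies (Section 3.2.1.1), and rollover is arranged to avoid a treatment gap (Section 3.1.1). Taking 13 weeks = 91 days of earlier treatment as an assumption, a rollover subject from a DS-5565 arm with the earliest permitted Visit 21 has 357 + 91 = 448 days, or 64 weeks. If earlier exposure counts, Step 2 applies only to de novo subjects and to rollovers without prior DS-5565.

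**Step 4: the two sentences side by side.** No other number precedes the desired number in Section 11.11, so it points back to the 500 exposed for at least 52 weeks. There are three ways to read the pair:

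- Both exact: a subject with 357 days has not completed 52 weeks, and the counts agree.
- Both nominal: Week 52 is a visit label, an in-window completer satisfies goal and rule alike, and the counts agree.
- Rule nominal, goal exact: the counts differ as in Step 2.

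Only the mixed reading produces the conflict, and nothing in the text favours it.

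**The case for a change.** The strongest reply is that each consistent reading requires choosing a definition the protocol does not supply, and that nothing later supplies it. Section 11 specifies no summary of extent of exposure; Section 11.3 reports those who completed the extension period, so completion is the count a reader will see. Visit 21 also serves as the early-termination visit, so attending it does not establish completion. Writing the definition down would take two or three sentences and no new data.

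It stands that the term is undefined and that the counts could diverge. It does not follow that closure would be decided on the wrong one. The rule is the sponsor's own forecast toward an approximate number, and nothing prevents that forecast from allowing for short exposures. The dates needed are available: Section 11.3 uses the date of first dose, and the follow-up contacts in Section 6.5 are timed from the last dose. A sponsor whose registration condition is stated as exposure has every reason to forecast exposure.

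Three supporting arguments carry little weight. Section 4.2.3 says "Subjects removed from the study for any reason will not be replaced", but a subject seen early within the window has not been removed. The repeated 500 is explained by the text: Section 11.8 counts across the programme and Section 11.11 states the goal of this study, so a shortfall here is not automatically a registration shortfall. Missed doses do not sharpen the problem either. The 80% standard in Section 5.1.2 applies to each visit interval and leads to counselling. With once-daily dosing on the nominal schedule (intervals of 7 days, six of 14, one of 21 and nine of 28) it allows as few as 6 + 6 × 12 + 17 + 9 × 23 = 302 doses, but neither the goal nor the closing rule is stated in doses taken.

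**Conclusion.** The day arithmetic is right, but the conflict is not established. It needs the closing rule read by visit label and the goal read to the day, whereas the paragraph reads naturally with a single count. Its size cannot be determined from the documents: the assumed early share of 0% to 46.7% includes no effect at all, and the resulting 500 to 267 subjects assumes that only extension exposure counts and that windows run from Visit 4. The study is descriptive, the target is approximate, and closure is a monitored forecast. The undefined term is missing detail that those running the forecast would fill sensibly by counting first to last dose and deciding how earlier DS-5565 exposure is treated. No change to the plan is needed.
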